# Project #1:

# Implementing Guidelines for Shared Decision Making in Lung Cancer Screening

## 1.0 Specific Aims

The goal of this project is to test two strategies for implementing shared decision making into clinical practice with the aid of the Decision Precision lung cancer screening tool. To accomplish this goal we have three aims:

**Aim 1:** To determine effectiveness of LEAP plus Audit and Feedback (A&F) versus A&F alone. **Hypothesis**: VAMCs with LEAP + A&F will have better implementation outcomes (defined by RE-AIM) than VAMCs with A&F alone.

**Aim 2:** To determine the effectiveness of allowing providers to set risk threshold algorithms. **Hypothesis**: Implementation outcomes will improve when providers are allowed to set risk thresholds.

**Aim 3:** To conduct a formative evaluation to determine the factors most important for successful implementation of risk-based shared decision making tools.

### 2.0 Rationale

Lung cancer is both prevalent and deadly. It is the third most common cancer and is the leading cause of cancer-related deaths in the US. Lung cancer is both more prevalent and associated with worse outcomes among Veterans than among the general US population.

Based on the results of the National Lung Screening Trial (NLST), the United States Preventive Services Task Force (USPSTF) recommends low-dose computed tomography (LDCT) screening for patients who meet age and smoking criteria. The NLST found that eligible heavy smokers are significantly less likely to die from lung cancer if screened with LDCT vs. chest x-rays. For perspective, the reduction in deaths from lung cancer with screening is larger than the reduction in deaths from the target cancers of other common screening tests, such as mammograms for breast cancer. In 2013, VHA rolled out a two-year clinical demonstration project in eight VA medical centers to determine the resources needed to "provide screening and follow-up...with accuracy, efficiency, and safety similar to that achieved in the NLST."

However, the NLST also found substantial harms associated with LDCT screening, including high false- positive rates which can lead to unnecessary and harmful invasive procedures. Because lung cancer screening has substantial benefits and harms, and the net benefit can vary dramatically across eligible smokers, the USPSTF strongly advocated for shared decision making and asserted that "the decision to begin screening should be the result of a thorough discussion of the possible benefits, limitations, and known and uncertain harms." Furthermore, in a February 5, 2015, decision memo, the Centers for Medicare and Medicaid Services (CMS) required a shared decision making consultation between patients and providers for payment of initial lung cancer LDCT screening. The role of shared decision making was specified within CMS guidelines as "including the use of one or more decision aids, to include benefits and harms of screening, follow-up diagnostic testing, over-diagnosis, false positive rate, and total radiation exposure."

Shared decision making (SDM) is the process wherein the provider communicates medical information about the screening options and patients are responsible for sharing their values and screening preferences. Following the sharing of information by both parties, patients and providers collaborate to decide on the course of screening that reflects both the best medical evidence as well as the patient's preferences and values.

The mandate for shared decision making by the USPSTF and CMS is reflective of the strong evidence that it can improve patient-centered outcomes. Research has found that *patients who participate in medical decisions tend to be more satisfied with their care*, *report a better quality of life*, *and are more adherent to recommendations* *than those who do not.* Furthermore, models of informed consent and SDM emphasize the importance of presenting the pros and cons of all treatment options to patients, and shared decision making is strongly advocated by many as an optimal method to promote patient-centered care, including in VA (e.g., 2006 priorities and patients' rights brochures).

To meet this need for shared decision making, we created "Decision Precision", a provider facing web-based decision support tool. This tool provides a method for providers to implement evidence-based guidelines for SDM in lung cancer screening. Our goal is to have the tool facilitate SDM within the confines of a busy clinical schedule. This web tool goes beyond current VA patient materials in several ways. It provides: 1) personalized

quantitative risk assessment of the trade-offs; 2) patient-friendly language; 3) graphics that have been empirically demonstrated to help patients understand their personalized risks and benefits; and 4) quick and easy documentation of personalized SDM after using the tool.

"Decision Precision" Tool Development. To determine the best method for communicating the benefits and harms of lung cancer screening, we first conducted a randomized survey experiment with 1,612 adults aged 18 years or older who reported smoking daily or almost daily. We compared comprehension and perception of lung cancer screening benefits and harms when the information was presented using four different evidence- based formats, including the pictograph currently used vin VHA's patient lung cancer screening materials. We found that participants who viewed the VHA pictograph had better knowledge about the magnitude of the benefit and how this benefit compared with important harms. Thus, we used the VHA pictograph in the tool. In addition, we iteratively designed four versions of the web tool based on usability testing with decision aid researchers, PCPs, and patients. The final version will be developed during Year 1 and will incorporate additional content and features suggested by front-line providers and patients, along with a module to enable personalized screening recommendations based on provider-determined risk thresholds.

# 3.1 Procedures

### 3.2 Proposed Implementation Strategies

We will compare the effect of adding the LEAP implementation strategy (see Implementation Core) to more typical and widely studied strategies that we will consider standard (i.e., audit and feedback and introductory webinar discussing use and benefits of the tool). We will also slowly roll out risk threshold tailoring to determine if that improves implementation outcomes.

#### Implementation Strategies: Control

1. *Webinar, Promotion, and Tool Access.* All sites will receive a professionally developed, 15-minute webinar that describes the tool's development (e.g., how the algorithm was designed) and a tutorial on how to use the website. We will promote the webinar and using the tool through key local leaders. A web-link to use the tool will be placed within the lung cancer screening clinical reminder.

2. *Audit and Feedback.* Due to the demonstrated importance of audit and feedback for changing provider behavior, we will deploy an audit and feedback system to all sites. This system will provide feedback on the screening and shared decision making process (e.g., number of provider's eligible patients screened for lung cancer, use of the tool, patient knowledge and satisfaction from patient surveys). When we visit the intervention sites to conduct usability testing (see below), our informationist from the Implementation Core will accompany us and meet with users to identify their needs and preferences for feedback (see Implementation Core). We will use this information to design an audit and feedback system to be implemented in all of the sites.

### Implementation Strategies: Two Interventions

1. An additional part of LEAP will be *user-centered design*. Prior to the implementation of the web-based tool, we will also visit the "intensive" implementation sites and conduct usability testing on the tool. Usability testing will be conducted with providers, nurses, lung cancer screening coordinators, and patients. We will go through the tool page by page to get feedback on the tool. We have done this in numerous studies and have specific protocols in place to do so. To the extent possible, we will use this feedback to modify the tool for these sites. Evidence suggests that when providers feel more engaged in the design of the tool, **they will be more likely to value and use it.** During this time we will also meet with the local Clinical Applications Coordinators to discuss adding a link to the Decision Precision website within clinical reminders.

2. *Risk Threshold Tailoring.* Providers at all sites will determine their own risk thresholds for making personalized recommendations within the tool. This will be done in a stepped-wedge design and will add a new site every two months until providers at all sites have been given the opportunity to tailor their thresholds. After completing a risk tailoring tutorial, they will identify two risk thresholds: 1) a low risk/low benefit threshold below which the provider would generally suggest that most patients not get screened (e.g., a number needed to screen of >500 to avoid one lung cancer death) and 2) a high risk/high benefit threshold above which they would generally suggest that most patients needed to screen of <100 to avoid one lung cancer death). In between these two thresholds is a gray zone where screening and not screening are presented as equally good options. We will provide significant leeway in allowing providers to make these cut-offs, but will impose certain constraints to make sure the thresholds do not violate professional standards. Of course, every screening recommendation will be accompanied by a recommendation for shared decision- making. We believe this strategy will address several potential barriers to implementation of clinical support systems—including provider's lack of

comfort with making decisions based on numeric risk-benefit information, lack of agreement with tool content, or a feeling of being taken out of the decision making process.

# 3.3 Study design and methods

Aim 1: To determine effectiveness of LEAP plus Audit and Feedback (A&F) versus A&F alone.

We will use multi-site, cluster-based randomization to evaluate the effect of the LEAP implementation strategy. Currently, there are eight VHA sites involved in the LDCT demonstration project and each site has agreed to be involved in our implementation initiative (see attached letters of support). We decided to only use these sites because they already have a successful lung cancer screening program in place and thus provide an ideal situation to test different implementation strategies for a decision support intervention. NCP will randomize which of the eight sites receive the LEAP implementation strategy.

Aim 2: To determine the effectiveness of allowing providers to set risk threshold algorithms.

Once the providers have experience with using the tool in practice, we can then start to roll out the risk threshold tailoring. We will roll this out at a rate which is limited by our capacity to do the tailoring and accompanying training in only one site at a time, but eventually reaching all of the sites by 18 months into the study. We will evaluate this additional part of the implementation strategy by comparing at different time points the sites that have received the training and tailoring to those who have not yet in what is effectively a stepped wedge analysis. Thus, we will enroll one site every two months into this strategy, stratified by whether the site is receiving the LEAP strategy, over 16 consecutive months.

**Evaluation Framework.** We will use the RE-AIM framework (Reach, Effectiveness, Adoption, Implementation, and Maintenance) to evaluate our two implementation strategies. Specific measures for the implementation evaluation are detailed in Table 2. Our primary goal is to determine whether these strategies lead to more frequent use of the Decision Precision Tool and align screening utilization with the magnitude of the mortality benefit from screening. While lung cancer screening is a preference sensitive decision and thus for any given patient, we cannot assess whether they made a "good decision", it is possible to evaluate the strength of the association between mortality benefit and screening utilization. If our tool is successful in communicating the benefit-harm information to providers and patients, we would expect that those with the largest potential to benefit would be more likely to be screened than those patients who have limited potential to benefit (we are calling this "precision decision making"). Based on these goals, our primary outcomes will be: 1) the proportion of eligible Veterans for whom the Precision Decision tool is used; and 2) ability of intensive implementation to provide precision decision making.

**Data Collection.** The majority of the data will be collected from Health Factors data within the VA Corporate Data Warehouse (CDW) and from 'paradata' automatically generated from use of the tool—i.e., data recorded by the website, which allows us to determine use of the various components of the Decision Precision tool. We should emphasize that paradata do not contain PHI—rather it includes which pages were viewed and for how long. Patients will also complete surveys to provide data for the audit and feedback system. We will query the Health Factors table on a weekly basis to identify patients who had initial screening conversations with a provider that week (i.e., clinical reminder completed) and will mail surveys to these patients.

RE-AIM Construct	Study Measures
Reach	Proportion of eligible patients with documented tool use after
Participation rate in the target population (patient level).	screening discussions (primary outcome).
Effectiveness (Aim 1)	Precision decision making (primary outcome)
The impact of the intervention on targeted outcomes.	High quality decision making
	Patient satisfaction with decision and process
Adoption (Aim 2)	# of tool assessments for each provider
Percent of providers who adopted the guidelines.	% of provider's eligible patients with documented tool use
Implementation (Aim 2)	# of tool assessments where:
The quality and consistency with which the guidelines	Patient decision aid was printed
were followed.	Shared decision making documentation was copied
	Dynamic pictograph depicting personalized benefit and
	harm was opened for display
Maintenance (Aim 2)	A re-assessment of each measure defined above will be
Degree to which the guidelines were followed over time.	completed during the maintenance phase.

# Table 2: Implementation Evaluation Measures using RE-AIM

**Outcome measures.** The outcome measures are specified in Table 2. The proportion of eligible patients with screening discussions is defined as those patients without documented exclusions for screening who have had initial lung cancer screening clinical reminders resolved. Documented tool use is defined as provider selection of the "use tool" radio-button that will be inserted into the clinical reminder ('Reach' construct). "Precision decision making" is defined as screening utilization aligning with Veterans' potential screening benefit. This will be estimated by inputting CDW data into a validated model. High quality decision making, obtained from patient surveys, will be defined as 1) adequate knowledge about the benefits and harms, and 2) values consistent with the screening decision. Additional outcome measures include decisional conflict,  patient perception of communication with physician,  participation in shared decision making,  and satisfaction with decision and decision making process.

**Power Considerations.** Our unit of analysis is site. Randomizing interventions by provider or PACT team is not feasible and would also likely result in significant contamination between arms. LEAP Strategy: Even with our small sample size (n=4 in each arm), we will still be able to detect an absolute difference of 25-35% from a control rate of 50% documented tool use, for an ICC of .05 to .10 and 400 total patients undergoing screening discussions in each site. We believe it would be necessary to see substantial differences in tool uptake in this range with the LEAP strategy relative to the control strategy to justify the resources that would be needed for widespread dissemination. We should note that it should be feasible to achieve this sample size as roughly 50 patients were eligible for the tool per month at each site during January, February, and March of 2015 (based on personal communication from NCP). Risk Threshold Tailoring Strategy: For this the stepped-wedge design with an average of 400 total patients undergoing screening discussions per site, we can detect a much smaller absolute difference in documented tool use of 7.5% from a control rate of 50%. We can also readily detect a small effect size (0.15 standard deviations) in any of our continuous variables.

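### The 7.5-point detectable difference for risk tailoring has no stated alpha, power, ICC or period handling; on a conventional period-adjusted reading it is about 8.1 to 8.5 points at 400 discussions per site

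*Combined protocol and SAP*

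**What the plan says.** The Power Considerations paragraph in section 3.3 (below Table 2) gives two detectable differences for documented tool use, which is a primary outcome.

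- **LEAP**, four sites per arm: "we will still be able to detect an absolute difference of 25-35% from a control rate of 50% documented tool use". The inputs named for this figure are "for an ICC of .05 to .10 and 400 total patients undergoing screening discussions in each site".
- **Risk tailoring**: the claim is that "we can detect a much smaller absolute difference in documented tool use of 7.5% from a control rate of 50" percent. The only input named for it, apart from the control rate, is in the words "For this the stepped-wedge design with an average of 400 total patients undergoing screening discussions per site". A further sentence gives 0.15 SD for continuous outcomes, which is the same quantity when the SD of a binary outcome is 0.5 (0.075/0.5 = 0.15).

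The design comes from the Aim 1 and Aim 2 text of section 3.3. On the number of clusters it says that "there are eight VHA sites involved in the LDCT demonstration project". For the roll-out the plan is that "we will enroll one site every two months into this strategy", and its length is given as "over 16 consecutive months". The evaluation is by "comparing at different time points the sites that have received the training and tailoring to those who have not yet".

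The Analysis paragraph specifies GEE clustered by site. Its terms are LEAP, risk tailoring and the patient's estimated lung cancer risk. It lists no calendar-period term. Alpha, sidedness and power are not stated for either figure, and an ICC is given only for LEAP.

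**The concern.** In a stepped wedge, tailored time falls late and untailored time falls early by design. Comparing tailored with not-yet-tailored sites at the same time means adjusting for period, and that adjustment costs precision. When the 7.5-point figure is recomputed with that adjustment and usual error rates, it comes out larger.

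This is the only planning figure for the effect of tailoring on tool use. If it is too favourable, a real gain of 7.5 points would be missed more often than the plan suggests, and a null result could be read as ruling out an effect that the study was not well placed to detect.

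**Working it through.** **Inputs from the plan.** 8 sites; one crossing every two months, so 8 steps; 400 discussions per site; control rate 50%, so total variance 0.25.

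**Assumptions.** ICC ρ = .05 to .10, borrowed from the LEAP sentence; two-sided 5%; 80% power (90% also shown); a constant site effect; categorical period effects; normal quantiles. The base layout has 9 periods (one before the first crossing, one after each), so m = 400/9 = 44.4 per site-period. Layouts of 8 and 10 periods are also shown.

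**Step 1: the LEAP figure, to see which conventions the plan might use.** Design effect = 1 + 399ρ = 20.95 (ρ = .05) or 40.9 (ρ = .10). Solve d = k × sqrt{[0.25 + (0.5 + d)(0.5 − d)] × DE/1600}.

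| Convention | k | LEAP, ρ = .05 / .10 |
|---|---|---|
| Two-sided, 80%, t on 6 df | 3.35 | 25.3 / 33.4 |
| Two-sided, 90%, normal | 3.24 | 24.6 / 32.5 |
| Two-sided, 80%, normal | 2.80 | 21.6 / 28.9 |
| One-sided, 80%, t on 6 df | 2.85 | 21.9 / 29.3 |
| One-sided, 80%, normal | 2.49 | 19.4 / 26.1 |

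The first two rows come close to 25-35; the one-sided 80% rows do not. One-sided 90% with t on 6 df (25.5 / 33.6) also comes close.

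**Step 2: the tailoring figure with period effects.** The stepped-wedge (Hussey-Hughes) variance with I = 8, T = 9 is

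Var = I·s·(s + T·τ) / [(I·U − W)·s + (U² + I·T·U − T·W − I·V)·τ],

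with s = 0.25(1 − ρ)/m and τ = 0.25ρ. Here U = 36 is the number of tailored site-periods, and W = V = 204 are the sums of squared column and row totals. The brackets are 8×36 − 204 = 84 and 1296 + 2592 − 1836 − 1632 = 420.

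- ρ = .05: s = 0.005344, τ = 0.0125; Var = 0.005038/5.699 = 0.000884; SE = 0.0297; 2.80 × SE = **8.3 points**.
- ρ = .10: s = 0.005063, τ = 0.025; Var = 0.009318/10.925 = 0.000853; SE = 0.0292; 2.80 × SE = **8.2 points**.

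Power at 7.5 points is Φ(0.075/SE − 1.96).

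| Periods | 80% power, ρ = .05 / .10 | 90% power | Power at 7.5 points |
|---|---|---|---|
| 8 | 8.2 / 8.1 | 9.5 / 9.4 | 72% / 74% |
| 9 | 8.3 / 8.2 | 9.6 / 9.5 | 71% / 73% |
| 10 | 8.5 / 8.3 | 9.8 / 9.6 | 70% / 72% |

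**Step 3: what moves the figure.**

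- *One-sided 5%, 80% power* (k = 2.49): 7.2 to 7.4 with 8-9 periods. This reaches 7.5 but does not fit the LEAP figures in Step 1.
- *No period terms*, as the Analysis paragraph reads: 5.4 to 5.9 with 8-9 periods.
- *Same-site correlation between periods at 0.9 of its within-period value* (s becomes s + 0.1τ, τ becomes 0.9τ; 9 periods, 80% power): Var = 0.001078 and 0.001260, giving 9.2 and 9.9 points.
- *Discussions needed for 7.5 points* (9 periods, 80% power): about 500 per site at ρ = .05 and 480 at ρ = .10.
- *Continuous outcomes* at the same ICCs: 0.0818/0.5 = 0.164 to 0.0833/0.5 = 0.167 SD.

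**The case against.** The strongest reply is that a figure with unstated inputs cannot be refuted by supplying other inputs. This stands. Besides one-sided testing, at least three period-adjusted routes reach about 7.5: an ICC near .25 at two-sided 80%; an ICC of 0 at 90% power (7.50); or a covariate that explains about 16-20% of the variance. The plan does say that covariates can raise power. But it gives no R-squared, and the first two routes lie outside the only ICC range it quotes. None can be excluded, and none is stated.

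The second reply is that the Analysis model as written has no period term and does better than 7.5. The arithmetic is right. That model does not match the concurrent comparison in Aim 2, however, and it would credit tailoring with any general rise or fall in tool use over the roll-out.

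The third reply is accrual. The plan quotes about 50 eligible patients per site per month, so 16 months would give 16 × 50 = 800. If all had discussions, the period-adjusted figure would be 5.8-5.9 points (9 periods). This softens the practical consequence. But the plan ties 7.5 to 400, and eligible patients are not the same as discussions held.

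Two stronger readings are tempting. A reader might infer that 7.5 points is flatly unattainable; the unstated inputs do not allow that. A reader might also carry the t on 6 df that fits LEAP over to tailoring and quote about 10 points. Six df is the between-site count for four against four sites, while the tailoring contrast is largely within site. With 55 df the figure is 8.3 to 8.5. Nor is that the only convention close to the LEAP range, since 90% power with normal quantiles also is. Whichever is used, applying a LEAP-compatible convention unchanged to tailoring gives about 9.4 to 10.1, not 7.5.

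**Conclusion.** The point holds as a modest understatement on the most natural reading, together with missing inputs. With two-sided 5%, 80% power, ICC .05-.10, period adjustment and a constant site effect, the detectable difference at 400 per site is about 8.1 to 8.5 points. That is 0.6 to 1.0 above the stated figure, with about 70-74% power at 7.5. At 90% power, or with between-period correlation at 0.9 of the within-period value, it is above 9. No convention close to the LEAP range gives 7.5 for tailoring once period is adjusted for.

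Error rates, the stepped-wedge ICC and the number of periods are my assumptions. The documents do not settle how the 7.5 was obtained, so this is not proof of a miscalculation. The mismatch between the Aim 2 comparison and the terms listed in the Analysis paragraph does not depend on those assumptions.

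**What to change.** 1. In Power Considerations, restate the tailoring figure as about 8 to 8.5 points at 400 discussions per site, and the continuous figure as about 0.16-0.17 SD. Alternatively, keep 7.5 points and state that it needs about 480-500 discussions per site. That is 60-63% of the 800 eligible patients implied by the quoted monthly rate over 16 months.
2. State the alpha, sidedness, power, ICC, number of periods and between-period correlation behind the figure. The last matters for the alternative in item 1, because extra patients help less when the correlation decays. At 0.9, even 800 per site gives about 7.2 (ICC .05) and 8.1 (ICC .10) points, by the Step 3 formula with m = 800/9.
3. Add calendar-period terms to the GEE model in the Analysis paragraph, so that the analysis matches the comparison described for Aim 2.

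This costs a few sentences and a slightly less favourable stated figure. It needs no change to the sites, roll-out or data collection.
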